7.5.8 Ophthalmological evaluation

Evaluation of your eyeball, eyelids, eyelashes, and other structures of your eyes by inspection, slit lamp (biomicroscopy), as well as palpation (touch). As part of this evaluation, visual acuity is taken with better corrected visual acuity, the integrity of the ocular surface is assessed, the anterior segment, intraocular pressure is taken, gonioscopy is assessed, and posterior segment (fundoscopy) is assessed.

7.5.8.1 Best-corrected visual acuity

Described in the 7.4.5.6 Best-corrected visual acuity

7.5.8.2 Best Corrected Visual Acuity Near

Described in the 7.4.5.7 Best Corrected Visual Acuity Near

7.5.8.3 Ocular Surface Integrity

This will be done by means of biomicroscopy using the slit lamp of the research center. An inspection of the cornea, conjunctiva, tear film, and eye stains with lysmine green and fluorescein will be carried out (in the section 7.4.5.8 SICCA Ocular Surface Staining stains are described.)

7.5.8.4 Previous Segment

It is the evaluation of the structures of the anterior segment [cornea, conjunctiva, anterior chamber, iris, pupil (includes measurement of pupillary diameter), lens, aqueous humor]. The evaluation will be made by means of the slit lamp.

7.5.8.5 Intraocular pressure

Described in the 7.4.5.1 Intraocular pressure

7.5.8.6 Gonioscopy

It is an assessment of the iridotrabecular angle by attaching a gonioscopy lens to the patient's cornea. In some cases, the lens will be filled with a high viscosity solution (2% hydromellose) to improve the coupling of it with your cornea.

For the classification of the angle, the Shaffer system will be used.

Board 2. Shaffer's classification

DEGREE	ANGULAR OPENING	DESCRIPTION	RISK OF OCCLUDING
4	45°-35°	Open	Impossible
3	35°-20°	Open	Impossible
2	20°	Narrow	Possible
1	≤ 10°	Extremely narrow	Likely
0	0°	Closed	Occluded

Angular closure or suspected angular closure shall be Grade 2 or less in more than 180° of the angular circumferences.

7.5.8.7 Posterior Segment (Fundoscopy)

Also called ophthalmoscopy. This is the test done with a light and a magnifying glass to look at the fundus (optic nerve and retina) through the pupil. Sometimes it will be necessary to dilate the pupil so that the fundus of the eye can be evaluated much better.

7.5.9 Application of Medications During Visits

During patient visits, different medications or medical devices may be applied to the ocular surface for ophthalmological examination.

Examples:

- Tetracaine 0.5% ophthalmic solution, used to anesthetize the patient and facilitate the measurement of intraocular pressure, application of dyes for staining and placement of the lens for gonioscopy.
- Ophthalmic solution of tropicamide 0.8% and phenylephrine 5%, used to dilate the pupil and better assess the posterior segment.
- Hydromellose ophthalmic solution 2%, may be used by the Investigator for the assessment of gonioscopy.

7.5.10 Delivery of material for the subject

It refers to the delivery of the subject's identification card and the subject's diary. The ID card will serve as an ID with the treatment assignment number; this card may serve as an appointment card. The Subject's Diary serves to keep track of the times the treatment is applied.

7.5.11 Delivery of Study Medication

Once the patient is in the study, the investigational product will be given, and the dosage of the product will be explained (one drop once a day at night in both eyes).

7.5.12 Evaluation of concomitant medicinal products

It is the question about the use of medications that they are taking regularly or that they have used in the last month. If you have required injected eye drug therapy, you should ask about the injected drugs in the last 6 months.

7.5.13 Assessment of adherence to treatment

It refers to indirectly evaluating the number of applications during the period between visits. To assess the approximate number of drops, the Subject's Journal can be reviewed to find out the applications registered.

7.5.14 Return of Study Medication

[figure not shown]
It refers to the return made by the research subject of the product under investigation.

7.5.15 Subject Journal Removal

It refers to the delivery made by the research subject of the subject's diary.

7.6 Study Diagram and Timeline

7.6.1 Study diagram

BV= Basal visit

SC = Safety Call

VF= Final visit. Evaluation of outcome variables

QD= Once a day

V1 = Visit 1

AO= Both eyes

7.6.2 Study timeline

Board 3. Study timeline

Procedures	VB D 1	V1 D 7 ± 1	VF D 16 ± 1	LLS D 21 ± 1
FCI Signature	X			
Medical history	X			
Eligibility Criteria	X			
Concomitant Drug Evaluation	X	X	X	
Urine pregnancy test	X			X
Vitals	X	X	X	
Best-corrected visual acuity	X	X	X	
Near Best Corrected Visual Acuity	X	X	X	
Pupillary diameter measurement	X	X	X	
Evaluation of fluorescein staining and lysmine green	X	X	X	
PIO	X	X	X	
Comprehensive ophthalmological evaluation	X	X	X	
Pharmacologic mydriasis (phenylephrine/tropicamide)	X			
Anterior chamber angle assessment (gonioscopy)	X			
Evaluating AEs	X	X	X	X
Subject and IP code assignment	X			
Eye comfort index	X			
Delivery of the PI and initiation of intervention	X			
Daily subject delivery	X			
Adherence assessment		X	X	
Return / evaluation of the subject's diary			X	
Return of PI			X	

Abbreviations: D, day; AEs, adverse events; FCI, informed consent form; LIS, security call; PI, research product; IOP, intraocular pressure; V, visit.

7.7 Procedures to be carried out per visit

Listed below are the procedures that will be performed at each visit, which may not show the optimal order for the Research Center. The investigator should order it according to his or her needs, and the needs of the study and sponsor.

The measurement of the pupillary diameter should always be done prior to pharmacological mydriasis in the case of the baseline visit and prior to the ophthalmological check-up at all visits. In the evaluation of adherence to treatment, it can be reviewed in the subject's diary.

7.7.1 Baseline visit

- Signing of informed consent
- Preparation of general and ophthalmological medical history
- Measurement of vital signs (temperature, blood pressure, heart rate, respiratory rate)
- Concomitant Drug Evaluation
- Pregnancy test (where applicable)
- Best-corrected visual acuity measurement
- Best Corrected Visual Acuity Measurement Near
- Pupillary Diameter Assessment
- Ophthalmological evaluation
- Fundus evaluation under pharmacologic mydriasis
- Evaluating the angle in the anterior chamber
- Fluorescein and Lysmine Green Eye Staining
- Intraocular pressure measurement
- Evaluation of adverse events
- Ocular Comfort Index (OCI)
- Subject Code Assignment and Research Product Delivery
- Submission of the subject's diary

7.7.2 Visit 1

- Measurement of vital signs (temperature, blood pressure, heart rate, respiratory rate)
- Concomitant Drug Evaluation
- Best-corrected visual acuity measurement
- Best Corrected Visual Acuity Measurement Near
- Ophthalmological evaluation
- Pupillary Diameter Assessment
- Fluorescein and Lysmine Green Eye Staining
- Intraocular pressure measurement
- Evaluation of adverse events
- Adherence Assessment

7.7.3 Final Visit

- Measurement of vital signs (temperature, blood pressure, heart rate, respiratory rate)
- Concomitant Drug Evaluation
- Pregnancy test (where applicable)
- Best-corrected visual acuity measurement
- Best Corrected Visual Acuity Measurement Near
- Ophthalmological evaluation
- Pupillary Diameter Assessment
- Fluorescein and Lysmine Green Eye Staining
- Intraocular pressure measurement
- Evaluation of adverse events
- Ocular Comfort Index (OCI)
- Adherence Assessment
- Return of the research product
- Return of subject's diary

7.7.4 Security Call

- Evaluation of adverse events

7.7.5 Unscheduled follow-up visits

At the request of the subject or personnel related to the study, unscheduled follow-up visits may be carried out for the reporting of adverse events or any situation that warrants it. During these visits, all pertinent data on the adverse events reported should be collected and, where appropriate, an appropriate management plan should be established.

7.8 Data collection

7.8.1 Source documents

Source documents are all written or printed records derived from automated processes (e.g., printouts of laboratory results issued by automated analysis equipment) where the information is recorded for the first time, and which is part of the permanent records of the subject's history. Examples of source documents are medical history, clinical evolution notes, laboratory reports, cabinet study reports, nursing notes, follow-up notes, surgery records, etc.

The PI is obliged to accept the monitoring of the information related to the study, audits, review by ethics and research committees, and inspections by the health authority, this obligation implies direct access to the source documents.

7.8.2 Electronic forms of data collection

All data related to the protocol will be captured through an electronic case report form (eCRF) by the investigation team staff. The data related to the protocol should NOT be captured directly in the eCRF but should be transcribed from the corresponding source document. This procedure allows monitoring to verify the information captured in the eCRFs. It is the responsibility of the researcher to ensure that the information is transcribed into the eCRFs in a correct, complete, and timely manner. It is understood that all data captured and sent by the eCRF to data analysis is approved by the Researcher.

7.8.3 Archiving

The data collected in this database is anonymous (it only stores the subject number together with other information of interest). The program used for data capture and storage covers the traceability requirements necessary for the execution of clinical studies. The data collected will be stored by the sponsor or the clinical research organization designated for this purpose and its storage will have a duration of 10 years. The records of assignments of subject number will remain in the participating institutions in charge of the PI or his work team and must be kept for at least 5 years.

8. Evaluation and management of adverse events

8.1 Regulation and regulations on adverse events

The registration and reporting of adverse events and incidents will be carried out in accordance with the guidelines established in NOM-220-SSA1-2016 and the international guidelines ICH E6. [36][47][48][49]

8.2 Definition of Adverse Event

According to the International Council on Harmonization (ICH), an adverse event (AE) is any unfavorable medical appearance in a clinical investigational subject who is administered a pharmaceutical product, regardless of causal attribution. [47] [48] [49]

Therefore, an AE can be any of the following: any unfavorable and unintentional disease, symptom, or sign (including an abnormal laboratory finding) that is temporally related to the use of a medical product, whether or not it is considered related to such a product; any new illness or exacerbation of an existing disease (worsening of the nature, frequency, or severity of a known condition); relapse of an intermittent medical condition (e.g., headache) not present at baseline; any deterioration in a laboratory value or other clinical test (e.g., electrocardiogram [ECG], x-ray) that is related to symptoms or that results in a change in study treatment or concomitant treatment or discontinuation of study medication. [47] [48] [49]

As defined in the previous paragraph, an adverse event is defined as any event that occurs during treatment with a drug or device. However, the definition can also be applied as any unwanted event that occurs during a clinical trial, including behavioral disorders. [49]

8.3 Use of adverse events as a study safety variable

Measuring the safety of the use of PRO-201 is paramount to the study, therefore, it is considered important to report any unwanted manifestations or diseases that occur during the study, regardless of whether or not the manifestation is considered to be related to the treatment under investigation. [49]

8.4 Definitions relevant to the classification of adverse events

Severity (serious/non-serious), also called seriousness (serious/non-serious). Serious or serious is defined as any event that: results in death, threatens life, requires hospitalization or prolongs hospitalization, is a cause of permanent or significant disability or disability, is the cause of alterations or malformations in the newborn, other medically important conditions.

Severity (mild, moderate, or severe). Mild is those that present with minimal symptoms, do not require treatment or suspension of the medication; moderate, when they interfere with usual

activities, without threatening the subject's life, require treatment and may or may not require discontinuation of the medication; severe, those that interfere with usual activities and require pharmacological treatment and discontinuation of the medication. [36][47][48]

Causality. It is the relationship that is assigned between the pharmaceutical product and the adverse event: certainly caused by the pharmaceutical product, there is clear evidence of causality, i.e. the adverse event reappears with the administration of the pharmaceutical product; probably caused by the pharmaceutical product, there is a high suspicion of causality but no direct evidence is available or it is considered unnecessary or dangerous, i.e. the reaction disappears when the pharmaceutical product is discontinued; possibly caused by the pharmaceutical, there is additional information to suggest that the cause may be due to another pharmaceuticals or disease; unlikely to be caused by the pharmaceutical product, there is a clear explanation of the origin due to the underlying disease or the use of another pharmaceutical product; conditional, there is a lack of data to issue a clear causality; non-classifiable, those for which once all possible information has been obtained about the adverse event, it remains unclassifiable. [36] [47] [48] [49]

8.5 Responsibilities of the researcher

It is the responsibility of the Investigator to verify AEs through questioning, pertinent physical examination, assessment of evolution, as well as appropriate medical and pharmacological management; as well as to follow up until the resolution or outcome and definitive discharge of the AE, following the definitions determined in national and international regulations. [36] [47] [48]

In the event of an AE or any event that puts the health and well-being of the subjects at risk, pertinent medical care will be provided, either at the research center or will be referred to the Hospital Center with the highest resolution power with which the research center has a medical care agreement. The PI will notify the sponsor's clinical monitor, according to the times established in national and international regulations. In the case of serious adverse events, it will notify the sponsor and record the corresponding information in the eCRF and in turn, inform the IRB and IC.

The attention of the AEs will be carried out according to the event care diagram (see Figure 4. Adverse Event Care).

The sponsor's final report will include the report of adverse events in compliance with current national and international regulations. [36] [47]

If the research subject debuts during their participation in the study with any chronic adverse event, such as diabetes or systemic arterial hypertension, they will be referred to the competent health professional for chronic treatment. The follow-up and termination of your participation will be in accordance with the stipulations of the ICH.

8.5.1 Recording of adverse events in the electronic case report form

The adverse event registry considers:

- Subject identification information such as: subject number, age, gender, and if applicable specify the eye.
- Information about the causality of the adverse event, its relationship to investigational products, or to another drug related to the study, as appropriate.
- Important date information:
 - Date on which the adverse event occurs.
 - Date on which the Principal Investigator becomes aware of it.
 - Date of resolution or outcome, as applicable.
- Information on diagnosis and clinical management.
- Record the outcome or resolution of the event:
 - Recovered/resolved without sequelae
 - Recovered/resolved with sequelae
 - Not Recovered/Unresolved
 - Subject who presented death due to the adverse event
 - Subject who presented death and it is judged that the research product may have contributed
 - Subject who presented death and this is not related to the product under investigation
 - Unknown
- Information about the investigational product or product associated with the Adverse Event, Incident, Adverse Incident, AMR or SRAM must be recorded. The information essential for registration is the generic name, distinctive name or code of the investigational product or of the product associated with the undesirable clinical manifestation; it will also be necessary to enter the data concerning the batch number, manufacturing laboratory, expiration date, dose, route of administration, start and end dates of administration and/or consumption, reason for prescription; according to whether it is an investigational product or drug (protocol in which the subject currently participates) or whether it is a drug that the research subject consumes for the treatment of underlying concomitant diseases or uses for the management of some transitory sign or symptom that does not correspond to the Natural History of the pathology that motivated its entry into the research protocol.
- Indicate whether the removal of the suspected product (of causing the event) eliminates the adverse event. Also indicate if a dose adjustment is made, if the event changes in terms of intensity or seriousness, persistence of the reaction. It is important to indicate whether in those subjects who are exposed again to the product, which had previously been suspended, the AD reappears.
- Information regarding concomitant pharmacotherapy. Indicate the generic name, dose, route of administration, start and end dates of use, as well as the reason for the prescription, regardless of whether it is in accordance with the prescribing information or technical data

sheet or is used outside the regulations or what has been authorized by the local, national or international regulatory entity.

- Relevant medical history information. The analysis of the AE considers the information previously narrated, despite the clinical context in which this harmful phenomenon occurs in the participants of the clinical research protocol, is of special interest, so the information about previous conditions, hypersensitivity or allergy phenomena, previous surgical procedures, laboratory analyses or cabinet examinations that have been performed on the participant, etc., that the researcher deems it appropriate to mention may do so.

8.5.2 Adverse Event Tracking

The Principal Investigator will provide care and follow-up of the adverse event presented by the participant until its outcome, according to what is referred to in the following section.

8.5.2.1 Diagnosis against signs or symptoms

Whenever possible, an AE should be assessed/reported as a diagnosis and not as a sign or symptom (e.g., liver failure or hepatitis rather than jaundice, asterixis, and elevated transaminases). If a diagnosis cannot be made from the signs or symptoms, then each sign or symptom should be recorded as an AE. If a diagnosis is made later, all AEs reported as signs or symptoms should be nullified and replaced by a single adverse event based on the diagnosis, with an onset date that corresponds to the onset date of the first symptom or sign of the eventual diagnosis.

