
Elimination criteria:
 
 – Withdrawal of the letter from the FCI. – Presentation of a serious adverse event related or not to the investigational product, which at the discretion of the PI and/or sponsor could affect the patient's ability to continue with the study procedures safely. – Non-tolerability or hypersensitivity to any of the compounds used during the tests (fluorescein, lysmine green, tetracaine). – No tolerability or hypersensitivity to the investigational drug. – Adherence < 90% determined by the subject's diary 	

Research Product (PI):
 
 - PRO-201 . Atropine Sulfate 0.01%. Zapopan, Jalisco, Mexico. Ophthalmic solution Laboratorios Sophia, S.A. de C.V - Dosage: 1 drop once a day (QD) in the evening, in both eyes (AO). - Route of administration: Ophthalmic 	

Duration of treatment: 14 days
	
Duration of the subject in the study: 21 days

Evaluation criteria:
 
Primary outcome variables
 
 – Incidence of unexpected PI-related AEs (Time of Assessment [TE]: days 7, 16 and 21) – Incidence of IP-related photophobia. (TE: 7th, 16th and 21st) 
Secondary outcome variables:
 
 – Changes in pupillary diameter (ET: day 7 and 16). – Incidence of expected PI-related AEs (TE: days 7, 16, and 21). – Changes in visual acuity (TE: day 7 and 16). 
Exploratory variables:
 
 – Changes in the AVMC (TE: day 7 and 16). – Intraocular pressure (IOP) changes (ET: day 7 and 16). – Changes in corneal and conjunctival staining with fluorescein and lysmine green (ET: day 7 and 16). – Changes in vital signs (heart rate and blood pressure) (ET: day 7 and 16). – Changes in the OCI (TE: day 16). 	

Statistical methodology
 
The analysis of the data collected in the study will be carried out using the SPSS version 19.0 statistical package. For continuous and discrete quantitative variables, data will be expressed by
	

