7.4.5.4 Photophobia

Photophobia is a sensory disturbance caused by light, it is considered a common symptom seen in neurological and ophthalmological conditions. According to Albilali (2018) it can be induced by glare; It was described as "uncomfortable vision, based on the diffusion of light through the ocular means or on a transient or permanent lack of adaptation." It involves an uncomfortable sensation of excessive brightness without pain, and occurs mainly with eye diseases, such as toxic, amblyopia, albinism, rod monochromatism, and corneal, lenticular, and vitreous opacities. In this study, it may occur secondary to pharmacological mydriasis generated using atropine sulfate. [42]

Photophobia will be assessed within the adverse event interrogation according to the 8. Evaluation and management of adverse events, without questioning in a directed way within visit 1, final visit and security call. It will be reported as present or absent.

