7.4.5.5 Pupillary diameter

It is the hole in the middle of the iris through which light penetrates the eyeball. Its diameter results from the balance between the pupil sphincter muscle and the radial fibers of the iris (pupil dilator). Normal values are 2-6 mm. [37]

In higher concentrations this product is mydriatic, however, due to the nature of the research and the physicochemical characteristics this reaction is not expected to occur, we will consider as significant the change that is generated in the pupil of the research subjects > 2 mm (pharmacological mydriasis), whether this change in photopic or mesopic vision. The method to perform the measurement will be using the following tool: OPD-Scan III (NIDEK CO., LTD, Tokyo, Japan). It is requested that the tool used be the same for all patients of the research center and for all their visits. It is necessary that the measurement is always done in the same office, with the same artificial light conditions and that the patient has at least 5 minutes inside the place before the measurement.

If there is a change greater than 2 mm between baseline and any of the other measurements, the product will be considered to have produced pharmacological mydriasis. This change will also be considered an adverse event.

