8.5.2.2 Adverse events secondary to other adverse events

In general, AEs secondary to other AEs (cascading events or sequelae) should be identified according to the primary cause, with the exception of serious events. A medically important AE secondary to an AE that is separated in time from the initial event should be reported as a separate event in the EA section of the eCRF. For example:

If vomiting results in mild dehydration without additional treatment in a normal adult, vomiting should only be reported on the eCRF.

If vomiting results in severe dehydration, both events should be reported separately on the eCRF.

If severe gastrointestinal bleeding leads to renal failure, both events should be reported separately on the eCRF.

If a dizziness event leads to a fall and subsequent fracture, then all three events should be reported separately in the eCRF.

If neutropenia is accompanied by infection, both events should be captured independently in the eCRF.

All EAs must register separately if there are concerns regarding the association of events.

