10.1.1 Calculation methodology

Atropine sulfate 0.01% has sufficient scientific evidence that confirms its efficacy and safety as an adjuvant in the treatment to delay the progression of myopia in children. In the meta-analysis carried out by Zhao et al (2019), in a sample of 1079 subjects from 7 clinical studies (505 in the 0.01% atropine group and 574 in the control), the incidence of AEs in 0.01% atropine sulfate was statistically lower compared to the control group [OR=0.26, 95% CI (0.11, 0.61)]. While, in the review by Li et al (2019), children who received 0.01% atropine had a better balance between the use of the treatment-incidence of AD, being well tolerated at this concentration (only 2% had photophobia). On the other hand, in the meta-analysis by Wang et al (2020), no study reported severe/serious AEs after administration of 0.01% atropine. Finally, the meta-analysis by Huang et al. (2016), in agreement with these results, mentions that low-dose atropine (0.01%) is one of the most effective interventions with a minimal prevalence of clinical symptoms. Considering this information and the primary objective of the study, the following proposal was made for the sample size. [52, 53, 54, 55, 25] [52] [25][53][54]

For one-arm clinical studies (*single-arm trials*) where the primary endpoint depends on the duration of the study (e.g., survival rate, AD incidence, etc.), there are options available in the literature for sample size calculation. The most common options are the *log-rank* and assuming exponential distribution. Another option for calculation is to use a parametric exact test, following a Chi-square distribution. [56]

The probability that a subject will experience no improvement during the study is given by:

$$d = \int_0^{\infty} G(t) \cdot f_1(t) dt$$

Where $F_1(t)$ is $f(t)$ with $\theta = 0.1$ (θ is a scale parameter, and β is the form of the parameter that determines the shape of the risk function [if $\beta > 1$ the risk increases over time, and if $\beta < 1$ the risk decreases over time, when $\beta = 1$ represents a special case of exponential distribution with constant risk]). Dividing the number of events by d given the sample size adjusted for possible losses. [56]

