10.1.2 Size Calculation

The PRO-201 ophthalmic solution is expected to be safe in its ophthalmic application when it has an incidence of unexpected, related AEs of less than 10%, and is tolerable when it has an incidence of photophobia that is less than 15% of the study population.

On this basis, a sample of 24 ophthalmologically and clinically healthy subjects was estimated. This value was increased by 20% considering possible losses. Based on this consideration, 29 subjects (who will contribute one eye, OD) are required to respond to the primary objective of the study.

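### The AE recoding rules in 8.5.2.1 and 8.5.2.2 can drop photophobia, a primary endpoint, because the protocol does not say which record gives the primary count

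*Combined protocol and SAP*

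**What the plan says.** The synopsis (1.1) lists as a primary outcome "Incidence of IP-related photophobia. (TE: 7th, 16th and 21st", the numbers being study days. Section 10.1.2 says the product "is tolerable when it has an incidence of photophobia that is less than 15% of the study population".

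Section 7.4.5.4 sets the route of collection: "Photophobia will be assessed within the adverse event interrogation according to the 8. Evaluation and management of adverse events". It describes photophobia as a symptom, adds that "In this study, it may occur secondary to pharmacological mydriasis generated using atropine sulfate", and asks for a present/absent result. Board 1 (7.4.4) classes it as an expected, product-related AE and makes it operational as present/absent.

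Section 7.4.5.5 treats a pupil change above 2 mm as pharmacological mydriasis and adds: "This change will also be considered an adverse event".

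Two recording rules in section 8 bear on this. Section 8.5.2.1 prefers a diagnosis to its signs and symptoms and says: "If a diagnosis is made later, all AEs reported as signs or symptoms should be nullified and replaced by a single adverse event". Section 8.5.2.2 says that, in general, "AEs secondary to other AEs (cascading events or sequelae) should be identified according to the primary cause, with the exception of serious events". Neither mentions photophobia.

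**The concern.** A general AE-logging convention is being applied to a symptom that is also a primary endpoint. Photophobia has no instrument of its own. The two schedules (1.3 and 7.6.2) and the visit lists (7.7.1 to 7.7.4) contain no photophobia item, only AE evaluation, and AE evaluation is the sole procedure at the safety call. A site that follows section 8 literally, faced with photophobia and a pupil change above 2 mm in one subject, could enter mydriasis alone and void the photophobia entry or never make it. The same could happen if the symptom were later explained by dry eye or allergic conjunctivitis, both of which 7.4.5.9 lists as possible events.

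Any such loss lowers the photophobia count and so favours the tolerability claim. An event that was never entered cannot be recovered at analysis.

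**Working it through.** **Does the text allow the loss?**

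1. *Source.* Section 7.4.5.4 sends photophobia through section 8, so section 8's recording rules apply unless something exempts it. Nothing does.
2. *Route through 8.5.2.2.* Section 7.4.5.4 itself describes photophobia as possibly secondary to mydriasis, and 7.4.5.5 makes mydriasis an AE. The carve-outs in 8.5.2.2 are serious events, medically important events separated in time, and doubt about the association. Mild photophobia concurrent with mydriasis fits none of them. The nearest of the section's own examples is vomiting with mild dehydration, where only the vomiting is logged. This is the more direct route.
3. *Route through 8.5.2.1.* This needs a diagnosis. Whether a measured pupil change is a diagnosis or a sign is open; dry eye or allergic conjunctivitis would plainly qualify.
4. *Conflicting text.* Section 7.4.5.4 and Board 1 require photophobia to be reported present or absent. Section 10.3.2 does not say which record the analysis reads.

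The loss is therefore possible but not certain, and it needs a mydriasis AE or another diagnosis in the same subject.

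**How much could it matter?**

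Plan's sample size (10.1.2): 24 × 1.20 = 28.8, rounded up to 29. This reproduces. The documents give no figure for photophobia lost through recoding.

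*Assumption A:* the criterion is an observed rate below 15%. The documents state no formal decision rule.

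- N = 29: 0.15 × 29 = 4.35, so at most 4 events pass. 5/29 = 17.2% fails; 4/29 = 13.8% passes.
- N = 24: 0.15 × 24 = 3.6, so at most 3 pass. 4/24 = 16.7% fails; 3/24 = 12.5% passes.

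In either case, one recoded subject at the boundary reverses the result.

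*Assumption B (hypothetical):* the true incidence is p, and a share q of cases is recorded only under another term. The recorded rate is p(1 − q). For p = 20% this is 20% × 0.75 = 15% at q = 0.25, and 20% × 0.50 = 10% at q = 0.50. The chance of passing is P(X ≤ 4), with X binomial(29, p(1 − q)):

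| True p | q = 0 | q = 0.25 | q = 0.50 |
|---|---|---|---|
| 2% (rate cited in 10.1.1) | about 100% | about 100% | about 100% |
| 15% | 55.5% | 77.8% | 93.8% |
| 20% | 28.4% | 55.5% | 84.2% |
| 25% | 11.5% | 34.3% | 70.7% |
| 30% | 3.8% | 18.6% | 55.5% |

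*Alternative to A:* an exact one-sided 5% test against 15% passes only 0 of 29, since 0.85^29 = 0.9%. The chance of a false claim at a true 15% is (1 − 0.15(1 − q))^29 = 0.9%, 3.1% and 10.4% for q = 0, 0.25 and 0.50.

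**The case against.** The strongest reply is that photophobia already has its own present/absent definition in 7.4.5.4 and Board 1, and its own line in Board 4, apart from the unexpected-AE and overall AE lines. On that view section 8 governs how the question is asked and how the log is kept, and the specific definition overrides the general convention. Section 7.4.5.9 also lists photophobia and mydriasis as separate expected events. The secondary-event rule is qualified as general, and four of its five examples record the events separately. Section 7.4.5.5 says mydriasis is not expected at this concentration, and 10.1.1 cites a review of children in which "only 2% had photophobia".

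Much of this stands, and it rules out three stronger readings that a reader might infer:

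- *Photophobia is removed from the count.* The documents do not say so. Photophobia with no concurrent diagnosis or primary-cause event stays in under both rules, and even where one exists the present/absent record may keep it.
- *The secondary expected-AE result collapses too.* It does not at subject level. A subject recoded to mydriasis, dry eye or allergic conjunctivitis still has an expected AE. Pupil diameter and near and distance acuity are also measured directly.
- *The 20% scenarios estimate the bias.* They are hypothetical. Neither the true rate nor the absorbed share is in the documents.

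The reply does not supply the missing link. No passage says that the primary count is read from the present/absent result, and no schedule or visit list provides a place to record it outside AE evaluation. An expectation that mydriasis will be rare does not settle the matter either, because 2.4.1 lists it as a risk at 0.01% and the criterion has to work if the expectation is wrong.

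**Conclusion.** The concern holds as a gap in the definition of a primary endpoint. Two instructions pull in different directions: report photophobia as present or absent, and replace or subsume symptoms and non-serious secondary events. The protocol does not say which one determines the primary count. If the AE log is used, cases can be lost, and only towards a finding of tolerability.

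The size is unknown. With the criterion read as an observed rate below 15%, there is no practical effect at the cited 2%. Close to the threshold one recoded subject is enough to change the conclusion. The probabilities in the table rest on assumed true rates, assumed absorbed shares and an assumed decision rule; they show sensitivity and are not a forecast. The point still merits correction before enrolment because it concerns a primary endpoint, the error runs one way, and records never entered cannot be rebuilt.

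**What to change.** 1. Add to both 8.5.2.1 and 8.5.2.2: *Photophobia is always recorded as its own event. It is never nullified or subsumed under a diagnosis or primary cause; any such diagnosis is recorded in addition.*
2. State in 7.4.5.4 that the primary count is taken from the present/absent photophobia record at visit 1, the final visit and the safety call. That record should carry a causality assessment, because the endpoint is product-related photophobia. Keep the undirected questioning that 7.4.5.4 specifies.
3. Provide an eCRF field for this record, and list it in the schedules and visit lists.

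The cost is a few sentences and one eCRF field, with no added visit or examination. The drawback is that some subjects will show both a symptom and its diagnosis, so AE event counts rise slightly. The number of subjects with any AE does not change.
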